dose/frequency, type of maintenance medication use (e.g. reduction/discontinuation in opiate use) also with real time, daily diaries. We will also examine whether or not MM patients experience loss of control over intake of marijuana or other substances. We will use measures such as development of tolerance, escalation of use, marijuana caving, and assess experience of reinforcing effects (e.g. euphoria or 'high'), and withdrawal among those who choose to stop using marijuana.

Any changes throughout 12 months in perception of disease symptomatology or in use of maintenance medication will be compared to the waitlist control group.

Aim 2: To assess neurocognitive and psychiatric effects of MM. We expect that neurocognitive outcomes, such as working memory, attention, executive function, anhedonia, amotivation, and decision-making, (when not acutely intoxicated) may be worsened with MM use. Outcomes may be worse in those who use more frequently/heavily (as measured by quantitative THC screens and dosing dairies).

Aim 3: In a subset of patients, assess how MM effects neurocircuitry of prefrontal function. We will use functional MRI tasks to assess working memory, inhibitory control, sustained attention, and risk/reward task performance and brain activation patterns. We expect that individuals who use MM may experience changes from baseline in neurocircuitry involved in memory, attention, inhibitory control and reward.

Aim 4: To assess how medical marijuana patients compare to healthy controls in structural and functional brain imaging measures. We will use functional MRI tasks to assess memory, inhibitory control, sustained attention, and risk/reward task performance and brain activation patterns. We expect that individuals who use MM to show alterations in task-related brain activity.

III. PARTICIPANT SELECTION

Medical Marijuana Participants

Inclusion Criteria:

1. Men and women aged 18-65 years, inclusive;
2. Competent and willing to provide written informed consent;
3. Desire to use medical marijuana for self-reported pain, sleep, or affective (mood and/or anxiety including PTSD) symptoms.
4. Not in possession of a medical marijuana card, but expressing intent to get one.
5. Able to communicate in English language.

Exclusion Criteria:

1. Current daily marijuana use (prior to enrollment)

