When participants in the active study group receive their medical marijuana card, they will be scheduled for a baseline assessment in which they will undergo cognitive testing, interviews, questionnaires, and possibly an MRI scan (see Measures below). In contrast, participants in the waitlist control group will be scheduled for the baseline visit approximately 3-4 weeks following the screening visit. All participants will then be scheduled for repeat assessments at approximately 2 weeks, 1 month, 3 months, 6 months and 1 year after the baseline visit. All participants will receive monthly check in phone calls from a research coordinator at approximately 2, 4, 5, 7-11 months past baseline in order to update study staff on medication changes, recent substance use, and overall physical and mental health. Participants will also be asked to complete a 2-year follow-up phone call, which is identical to previous check in calls, with the addition of the CGI and CUD checklist. If participants are in the active study group, we will ask that they not use MM on the day of testing (though they can use it after testing on that day). These visits will take approximately 3 hours to complete.

In consultation with their prescribing physician, participants in the waitlist control group will be asked to wait to start using MM until they have completed Visit 5 (Three Months). During those 3 months, they will be assessed at the same time points as those in the active MM group (see study schema). After the 3-month waitlist period, the waitlist control group will have the option to start using MM. If this group fails to adhere to the waitlist control, they will be kept in the study and will be asked to complete the same assessment schedule as those initially assigned to the active study group. All participants will be assessed after 1 year.

Measure	Instrument	Visit 1	Visit 2	Visit 3	Visit 4	Visit 5	Visit 6	Visit 7
		Screen	Baseline	Two Weeks	One Month	Three Months	Six Months	One Year
General Medical/Psychiatric Health								
Medical History/ CON MEDS		x	x	x	x	x	x	x
Quantitative cannabinoids			x	x	x	x	x	x
Drug Screen/pregnancy		x	x	x	x	x	x	x
Psychiatric Interview	MINI 7 + Past SUD and AUD	x						x
Suicidality and Health Risk Taking	CHRT	x	x	x	x	x	x	x
Emotional and physical Functioning	SF-12		x	x	x	x	x	x
ADHD symptoms	ASRS		x					x
Impulsivity	BIS-11		x			x	x	x
Executive function	BRIEF		x			x	x	x
Risk perceptions and behavior	DOSPERT		x			x		

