Family history of Addiction	KSADS	x						
Provider Expectations for Recovery Scale	PERS	x						
Substance Use								
Frequency of substance use	TLFB (MJ, EtOH, tobacco, other drugs)	x	x	x	x	x	x	x

Cannabis Use Disorder Screen	DSM-5 Cannabis Use Disorder Checklist	x	x	x	x	x	x	x
MJ craving	MCQ-SF		x	x	x	x	x	x
Marijuana Motives	MMM					x		
Marijuana Withdrawal (if stop)	CWS		x	x		x	x	x
MJ use severity	CUDIT		x	x	x	x	x	x
Harmful drinking	AUDIT	x				x	x	x
Alcohol consumption urge	URGE		x	x	x	x	x	x
Expectancy of MMJ effects	MMEEQ	x	x		x	x	x	x
Reflection of MMJ effects (qualitative)							x	x
Symptoms								
Pain level	BPI	x	x	x	x	x	x	x
Pain Catastrophizing Scale	PCS	x	x	x	x	x	x	x
Perceived Stress Scale	PSS	x	x	x	x	x	x	x
Clinician's Severity Scale	CGI		x	x	x	x	x	x
Insomnia	AIS	x	x	x	x	x	x	x
Anxiety Scale	HADS	x	x	x	x	x	x	x
Delusions and Psychosis	PDI		x		x	x	x	x
Difficulties due to health conditions	WHODAS	x	x			x	x	x
Post-traumatic stress symptoms	PCL	x						x
COVID-19 Specific Questionnaires								
Remote Pre-Visit Form	PVF	x	x	x	x	x	x	x
Effects of COVID-19 pandemic on mood, pain, sleep, lifestyle	COVID Impact	x	x	x	x	x	x	x
Impact of epidemic/pandemic on various areas of life	EPII	x						
Changes in substance use since COVID-19 pandemic	Covid19-CSU	x						
Cognitive Testing								
Verbal learning/memory, attention, working memory, and complex decision-making	CANTAB		x		x	x	x	x
Intelligence / reading	WTAR	x						
MRI Scan								
MPRAGE	Structural		x					x
Resting state	Functional connectivity		x					x
Task-based (i.e. working memory, inhibitory control)	Task-based fMRI		x					x

Drug Testing: At all study visits, participants will provide a urine sample, which will be used to qualitatively screen for cannabis use as well as other substances of abuse. For participants who provide written consent for sample shipment, urine samples will be shipped to quantitatively screen for amount of THC metabolites in urine. Samples will only be shipped for participants who report recent marijuana use and/or qualitatively screen positive for THC. An alcohol reading may also be taken if there is any concern about a participant being intoxicated.

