Power/Sample Size. Aim 1 seeks to address the development of CUD (dependent on the number of symptoms reported) in the MM compared with the WLC group. To assess this, we will use the DSM-5 criteria for CUD, which combines the DSM-IV categories of abuse and dependence into a single disorder measured on a continuum from mild to severe. We have based power sample size requirements on the between and within subject ANOVA of the dependent variable of CUD symptoms, comparing the MM versus WLC conditions tested across the baseline to 3 month periods, where the primary effect of interest is the condition X time interaction. A power analysis using the Gpower computer program²⁹ indicated that a sample of 80 participants per group would be needed to detect small to medium effect (Cohen's $d=.3$) with 90% power using a t test with alpha at .05.

Data Analysis Plan: In general, 3 analytic approaches will be employed, corresponding to three types of comparisons and data:

(a) Numeric Data Assessed at Baseline, 3 Months, 6 Months and 1 year. Measures of addiction, tolerance, and cognitive performance will be analyzed with a between- and within-subject analysis of covariance, the primary between-subject factor being Condition, i.e., the active MM vs. WLC group, and the within-subject factor being time, i.e., assessments at baseline and 3 months. Relevant subject-level numeric covariates (i.e. THC metabolite levels) and categorical factors (e.g. disease category) crossed with condition and possibly interacting with time will be included in the analysis. Covariates such as baseline MJ use, primary disorder for which MM is sought, age, and gender will be of interest. The term of primary interest will be the interaction of condition x time as a test of the hypothesis that assignment to the MM condition will be associated with an increased rate of CUD. A limited amount of backward elimination of nonsignificant ancillary terms will be employed to increase power for effects of more interest (e.g. non-significant terms can be dropped from the models). An additional, analogous repeated-measure ANCOVA, restricted to the MM group, will include the third

assessment at 6 months. The Greenhouse-Geisser adjustment for correlated error will be employed for significance tests with more than one degree of freedom. For all models, residuals will be checked graphically for adherence to assumptions of normality and homoscedasticity, and data transformations applied if needed.

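### The 6-month cognitive analysis uses the medical marijuana arm alone, so its time effect cannot separate retest practice from a drug effect, although the waitlist arm is scheduled for the same tests

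*Combined protocol and SAP*

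**What the plan says.** Data Analysis Plan (a) sets the method for three kinds of outcome: "Measures of addiction, tolerance, and cognitive performance will be analyzed with a between- and within-subject analysis of covariance". The between-subject factor is MM versus WLC, with "the within-subject factor being time, i.e., assessments at baseline and 3 months". The plan continues: "The term of primary interest will be the interaction of condition x time", although the hypothesis attached to that term names only cannabis use disorder.

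Six months enters through a separate model: "An additional, analogous repeated-measure ANCOVA, restricted to the MM group, will include the third" assessment, at 6 months. The heading of (a) also names 1 year, but no 1-year model is described under it.

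Both arms attend the later visits. Study Design says: "All participants will then be scheduled for repeat assessments at approximately 2 weeks, 1 month, 3 months, 6 months and 1 year" after baseline. The measures table has one schedule for both arms and lists CANTAB ("Verbal learning/memory, attention, working memory, and complex decision-making") at baseline and at 1, 3, 6 and 12 months. No alternate forms, practice correction or retest norms are mentioned. The healthy-control schedule contains no CANTAB.

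Two further statements bear on the reading. Aim 2 expects that neurocognitive outcomes "may be worsened with MM use". And for the waitlist arm: "After the 3-month waitlist period, the waitlist control group will have the option to start using MM".

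The Summary of Changes lists cognitive testing as a secondary outcome over baseline to 12 weeks. It describes an amended model with one constant treatment effect across 2 weeks, 1 month and 3 months. It does not withdraw the 6-month MM-only analysis.

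**The concern.** Within one arm, change over time on a repeated cognitive battery is the sum of whatever practice adds and whatever the drug does. The two cannot be separated without a group that takes the tests without the drug, or an external estimate of practice. The plan supplies neither at 6 months, although WLC scores are scheduled to be collected then.

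The direction matters. Aim 2 looks for worsening, while practice tends to raise scores, so the error runs toward missing harm.

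Elsewhere the protocol deals with the same issue. The MRI section adds non-using controls, rescanned at 1 year, to gauge normal change over time. Aim 1 promises a waitlist comparison through 12 months for symptoms and maintenance medication. Neither provision is extended to cognition after month 3.

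**Working it through.** The plan states no power or effect size for this analysis, so there is no figure to reproduce. The check has a textual part and an illustration.

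**Text.** At 3 months, (a) uses both arms. At 6 months, (a) uses MM only, while Study Design and the measures table schedule both arms for CANTAB.

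**Inputs, all assumed.** g = practice gain and h = true harm, in SD units. Retest correlation r = 0.7, n = 100 per arm, two-sided 0.05, normal approximation.

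**Formulas.**
- SD of change = √(2(1 − r)) = √0.6 = 0.775.
- MM-only: expected change = g − h; SE = 0.775/√100 = 0.0775; P(significant decline) = Φ((h − g)/SE − 1.96).
- MM versus WLC to 3 months: expected difference in change = (g − h) − g = −h; SE = 0.775 × √(2/100) = 0.1095.

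**MM-only result with h = 0.3.**

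| g | Expected change (SD) | P(significant decline) |
|---|---|---|
| 0 | −0.3 | 97% |
| 0.1 | −0.2 | 73% |
| 0.2 | −0.1 | 25% |
| 0.3 | 0 | 2.5% |
| 0.4 | +0.1 | 0.1% |

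Worked row, g = 0.2: 0.1/0.0775 = 1.29; 1.29 − 1.96 = −0.67; Φ(−0.67) = 25%. With h = 0.2 and g = 0.4, the chance of a significant apparent gain is 73%.

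**Controlled 3-month contrast, h = 0.3.** 0.3/0.1095 = 2.74; 2.74 − 1.96 = 0.78; power 78%, whatever g is, because practice common to both arms cancels.

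**Dependence on n and r.** The documents allow other arm sizes: 2:1 allocation of 200 gives 200 × 2/3 ≈ 133 in MM, and Screening mentions 200 per group. For h = 0.2 and g = 0.1, with r from 0.6 to 0.8, P(significant decline) in MM alone is 20–35% at n = 100, 25–45% at n = 133 and 35–61% at n = 200. When g = h the expected change is zero and the probability is 2.5% (one tail of the 5% test) at every n. A larger sample does not remove the confounding.

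**What adding WLC at 6 months achieves.** Let c be the share of WLC that has started MM by then with the same effect (not given; assumed). The expected contrast is h(1 − c). With h = 0.3, r = 0.7 and n = 100 per arm:

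| c | Contrast (SD) | Power |
|---|---|---|
| 0 | 0.30 | 78% |
| 0.25 | 0.225 | 54% |
| 0.5 | 0.15 | 28% |
| 0.75 | 0.075 | 10% |
| 1 | 0 | 2.5% |

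Including WLC takes shared practice out of the estimate, but it does not restore an unexposed control.

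**The case against.** The strongest reply is that WLC participants may start MM after month 3, so they are not an unexposed comparator at 6 months. The plan does not give this as its reason for the restriction, but it is a plausible one. It stands as a limit on the 6-month contrast, as the dilution table shows. It does not make the single-arm time effect interpretable.

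Second, the main cognitive comparison is already controlled to 3 months, the listed outcome ends at 12 weeks, and the 6-month model is described as additional. All true, and this keeps the point modest. The 6-month model nevertheless remains in the plan, is not labelled descriptive, and is the only 6-month cognitive analysis in (a).

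Third, the parent model may include THC metabolite level as a covariate, possibly interacting with time. A practice gain common to all MM participants would not confound such an exposure-by-time term. That is correct, so the point concerns the main effect of time. The exposure term is only a possibility in the plan, and amount of use is not randomised.

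Fourth, every input to the illustration is assumed. This stands: the figures show the mechanism and do not predict this trial's result.

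Some stronger readings are not supported:
- A reader might infer that the sponsor will present the 6-month result as showing no cognitive harm. No passage says so.
- Calling the 6-month visit the third assessment might look like a miscount. It fits a baseline, 3-month and 6-month model, although it is the fourth CANTAB sitting.
- Remote testing or regression to the mean might be added as sources of bias. The documents do not say that CANTAB was given remotely, and eligibility does not select on cognitive scores.
- The diluted 6-month contrast might be called conservative. For a question about harm, bias toward zero reassures falsely.

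**Conclusion.** The point holds in a limited form. The MM-only time effect at 6 months cannot distinguish practice from an MM effect, and it can conceal the worsening Aim 2 looks for. Under the assumed values, detection of a 0.3 SD harm falls from 97% to 25% with a 0.2 SD practice gain. It falls to 2.5% when gain equals harm, and that last figure does not depend on sample size or retest correlation. The actual size is unknown, because the documents give no practice effect, retest correlation, WLC uptake or 6-month retention.

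The 3-month comparison is not affected, since shared practice cancels both in condition by time and in the amended constant-effect model. That contrast has its own caveat: the Summary of Changes reports differential drop-out between randomisation and baseline. This is a worthwhile, inexpensive improvement to a supplementary analysis, not a defect in the trial's main comparison.

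**What to change.** Amend Data Analysis Plan (a) as follows.

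1. Base any causal conclusion on cognition on the randomised MM versus WLC contrast from baseline to 3 months.
2. Fit the 6-month and 1-year model to both arms as randomised, with categorical visit and arm × visit.
3. Report the share of WLC that has started MM by each visit.
4. Label the difference after month 3 as immediate versus optional deferred access. State that WLC uptake biases it toward no difference, so a null result is not evidence of safety. Do not make it the main cognitive result.
5. Report within-MM change at 6 months as descriptive only, beside WLC visits made before any MM use. Beyond month 3, treat those visits as a non-randomised reference for retest change, because starting MM is then the participant's choice.

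The cost is a change of analysis wording and a little more analysis work, on assessments already in the schedule. The downside is that WLC uptake dilutes the 6-month contrast. In the illustration, power for a 0.3 SD harm falls from 78% to 28% if half of WLC has started MM.

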(c) Imaging Data. Imaging data will be analyzed using standard analysis platforms for longitudinal analysis (e.g. FSL and SPM). We will use a linear mixed-effects model approach, with a univariate two-stage specification. The advantage of this method is that it offers flexibility in handling unbalanced repeated measurements with missing data, which is one of the biggest challenges to longitudinal fMRI datasets. At the subject-level, a unique trajectory for each individual is defined for each region or voxel being considered, meaning that activation measurements are condensed into summary statistics for each scan. At the second, population-level, individuals are considered as arising from a population of all such individuals, each with a unique intercept and slope, and a linear mixed-effects model is fit. With this modeling approach, it is reasonable to deduce that the within-individual variances are the fluctuations around the individual-specific trajectory, and the among-individual variances can be described as differences of parameters characterizing these trajectories. As one way to conduct this model using brain-imaging data, statistical measures of brain activity responses serve as the dependent variable and one linear mixed-effect model is then fit for each ROI or voxel. Repeatability of fMRI can be directly addressed via certain parameters of this model.

Risks and Discomforts

Psychosocial risks

Risks: There are no legal risks to the participants associated this study, because medical marijuana is legal in Massachusetts. There is a small social risk associated with participation in this study, as some people may be embarrassed if others found out that they are using medical marijuana.

Minimization: All data will be completely deidentified and anonymized. Please see ‘confidentiality and loss of privacy’ below.

The Co-Investigators on this project include a psychiatrist ([name]) and a clinically-trained clinical psychologist ([name]). If there are any concerns about a subject who is actively suicidal and in need of clinical attention, the PI will be made aware of the issue immediately and will consult with appropriate medical personnel (co-investigators [name] and [name]) to determine appropriate steps. The PI and medically trained co-investigators will assess the needs of the subject and offer the subject either prompt treatment or medical referral, whichever is appropriate

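### The only stated 6-month model, an MM-only Greenhouse-Geisser ANCOVA, implies complete cases and leaves out the 2-week, 1-month and 1-year visits

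*Combined protocol and SAP*

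**What the plan says.** Part (a) of the Data Analysis Plan is headed "Numeric Data Assessed at Baseline, 3 Months, 6 Months and 1 year". Its main model compares the arms, with "the within-subject factor being time, i.e., assessments at baseline and 3 months". It then adds a second model: "An additional, analogous repeated-measure ANCOVA, restricted to the MM group, will include the third", continuing "assessment at 6 months. The Greenhouse-Geisser adjustment for correlated error will be employed for significance tests with more than one degree of freedom". Part (a) gives no rule for missed visits and includes no model for 1 year.

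The Study Design section schedules "repeat assessments at approximately 2 weeks, 1 month, 3 months, 6 months and 1 year after the baseline visit". In the table of measures, the "DSM-5 Cannabis Use Disorder Checklist" is marked at every visit, and the CANTAB at baseline, 1, 3 and 6 months and 1 year.

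Part (c), on imaging, chooses linear mixed-effects models and gives a reason: "The advantage of this method is that it offers flexibility in handling unbalanced repeated measurements with missing data". Part (b), on the daily diaries, also uses mixed models but does not cite missing data.

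The Statistical Analysis paragraph of the Summary of Changes says the IRB protocol lacked the final plan. It describes a revised model: a constant treatment effect over 2 weeks, 1 month and 3 months, adjusted only for baseline symptoms. It does not mention 6 months or 1 year.

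**The concern.** A classical repeated-measures ANCOVA with a Greenhouse-Geisser correction takes one complete set of values per person. With three time points and no imputation rule, someone who misses month 3 or month 6 contributes nothing, even if the other visits were attended.

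The waitlist group may start medical marijuana after 3 months, so the MM group's own course is the main planned information on later CUD symptoms and cognition. A complete-case result describes only those who attended all three visits. It loses precision whenever visits are missed, and it can be biased if leaving is related to how symptoms develop. Values already scheduled for collection at other visits are left out.

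**Working it through.** **1. Visits scheduled and visits used**

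| | Baseline | 2 wk | 1 mo | 3 mo | 6 mo | 1 yr |
|---|---|---|---|---|---|---|
| CUD checklist scheduled | yes | yes | yes | yes | yes | yes |
| CANTAB scheduled | yes | no | yes | yes | yes | yes |
| Part (a), between arms | yes | no | no | yes | no | no |
| Part (a), MM group only | yes | no | no | yes | yes | no |
| Revised model, front matter | as covariate | yes | yes | yes | no | no |

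From baseline on, the MM-only model uses 3 of 6 scheduled CUD assessments and 3 of 5 cognitive assessments. No row reaches 1 year, and only the MM-only row reaches 6 months. Three time points give a 2-df time test, which is where the Greenhouse-Geisser adjustment applies.

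**2. Share of participants kept**

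The plan has no figure of its own to reproduce here: the 80 per group in the power paragraph concerns baseline to 3 months. The documents give no post-baseline loss, so a range is assumed. If a fraction m is lost at month 3 and the same fraction of the rest at month 6, the share kept is (1 − m)².

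- m = 0.15: 0.85² = 0.7225, so 28% are dropped.
- m = 0.20: 0.80² = 0.64, so 36% are dropped.

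These are shares of people with a baseline visit.

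**3. Standard error of the 6-month change**

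Assumptions: continuous outcome, SD 1 at each visit, loss completely at random, no return after leaving. The correlations r03, r06 and r36 link baseline, month 3 and month 6. The comparator is likelihood on the same three visits.

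- Variance of the change: V = 2 − 2·r06.
- Part explained by baseline: E0 = (1 − r06)².
- Further part explained by month 3: E3 = (r36 − r03·r06)² / (1 − r03²).
- Remainder: R = V − E0 − E3.
- Complete-case variance × n: V / (1 − m)².
- Likelihood variance × n (large sample): R / (1 − m)² + E3 / (1 − m) + E0.

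Correlations 0.6 / 0.5 / 0.7: V = 1, E0 = 0.25, E3 = 0.40² / 0.64 = 0.25, R = 0.50.

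- m = 0.15: 1/0.7225 = 1.384 against 0.692 + 0.294 + 0.250 = 1.236. SE ratio √(1.384/1.236) = 1.06.
- m = 0.20: 1/0.64 = 1.563 against 0.781 + 0.313 + 0.250 = 1.344. SE ratio 1.08.

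All correlations 0.5: E3 = 0.25² / 0.75 = 0.083, R = 0.667.

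- m = 0.15: 1.384 against 0.923 + 0.098 + 0.250 = 1.271. SE ratio 1.04.

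Simulation with the first set (133 people) agrees: 0.104 v 0.098 at 15% (ratio 1.06) and 0.110 v 0.101 at 20% (1.09). A repeat gave 0.103 v 0.096 (1.07) and 0.111 v 0.102 (1.09). Hence roughly 4–9%.

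That range is for people who leave for good. If visits are missed independently, likelihood also keeps those who miss month 3 but attend month 6, and the gap is wider. A simulation with correlations of 0.5, 100 people and 20% missing at each visit gave 0.122 v 0.107, or 14%.

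**4. Bias**

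Suppose leaving before month 6 depends only on the month-3 score, which shifts the mean of that score among stayers by δ (negative if high scorers leave). With linear regressions the complete-case change is off by (r36 − r03)·δ. Its sign therefore depends on which correlation is larger. Simulated with 20% loss per visit, log-odds 0.7–1.0 per SD and a true change of 0.40:

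| r03 / r06 / r36 | Complete-case change |
|---|---|
| 0.6 / 0.5 / 0.7 | 0.382–0.386 |
| r36 = r03 (0.6 / 0.5 / 0.6 or 0.7 / 0.5 / 0.7) | 0.400–0.402 |
| 0.7 / 0.5 / 0.6 | 0.415–0.417 |

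If 20% instead miss month 6 because of a larger rise from baseline to month 3, the complete-case change is 0.31 (equal correlations of 0.5) or 0.21 (autoregressive, 0.7). Likelihood recovers 0.40, because loss there depends only on observed values.

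**The case against.** The strongest objection is the status of the text. The Summary of Changes says the protocol was written for a pilot phase and lacked the final plan. It calls the replaced approach a random slopes analysis, which is not the ANCOVA of part (a), so part (a) may not have been the working plan. This stands in part: silence about month 6 does not prove that the ANCOVA was kept. But no other 6-month model is stated.

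Several stronger readings are tempting, and the documents do not support them.

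- **The plan orders deletion of incomplete participants.** It does not say so; complete cases are implied by the method and the lack of a missed-visit rule.
- **The plan uses mixed models elsewhere because of missing data.** Only the imaging section gives that reason.
- **The 6-month change will be understated.** The bias can be nil or in either direction.
- **About 133 MM participants would fall to 96 or 85.** That takes two-thirds of 200 randomized people. An active-arm baseline visit is scheduled only once the card is received, and the front matter admits differential loss before baseline. The share dropped applies to a smaller, unstated number.
- **The main result is at risk.** The primary CUD outcome runs from baseline to 12 weeks, and the power paragraph frames the CUD question over 3 months. The 6-month model is additional and single-arm.

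The calculations also use continuous data. The sample-size section expects mean CUD symptom counts of 0.1 to 0.4, so the precision gain is not shown for that outcome.

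**Conclusion.** The point holds in a limited form. The one stated 6-month model implies complete cases at three visits and ignores the other scheduled visits. The described revision supplies no 6-month or 1-year replacement.

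Under an assumed 15–20% loss at each of two visits, 28–36% of those with a baseline visit would be dropped. The cost in standard error is roughly 4–9% for continuous outcomes and permanent dropout. Precision is lost whenever visits are missed; the presence and direction of bias cannot be determined from the documents. The 12-week primary test is not affected. This is a worthwhile, low-cost improvement to a later, additional analysis.

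**What to change.** For the 6-month and 1-year MM-group results, replace the repeated-measures ANCOVA with likelihood-based mixed models on every available visit from baseline to 1 year:

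- for CUD symptoms, a count model with a person-level random effect;
- for cognition, a linear mixed model;
- visit as a categorical term, with a simpler covariance named in advance as fallback if the unstructured one does not converge.

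Report the 6-month and 1-year changes with confidence intervals. State the missing-at-random assumption and add a sensitivity analysis for departures from it.

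The cost is plan wording, new code and somewhat more modelling work; no new data are needed. Convergence may be difficult with sparse counts. The change does not repair loss between randomization and baseline, which needs its own treatment.
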